12 DATA AND SAFETY MONITORING

This study will have a Data and Safety Monitoring Board (DSMB). The DSMB will meet regularly to review reports of all adverse events. The DSMB may review all procedures, protocol changes, ICFs and annual reports. Notification of all Serious AEs will be sent to DSMB, the principal investigator and the study's Steering Committee (comprised of research project leaders). The DSMB Chair also will function as an independent medical monitor and AE adjudicator. AEs will be reviewed and categorized as serious, non-serious, drug related, or procedure related. Based on the safety data, the DSMB has the authority to request a modification to the study design. This overview is only meant to be used as a guideline by the DSMB to review the study and to make a recommendation to continue or modify the protocol, not necessarily a mandate to the board for study termination. The members will not be involved in the planned study but will have the requisite clinical expertise to oversee subject safety. The DSMB will meet at least once per year, will review a written report prepared annually by the study team, and in response, will prepare a written report of the results of these meetings. The PI will alert the DSMB,

along with the IRB, the study's Steering Committee, and the NHLBI Program Officer of any serious AEs. Procedures and requirements for prompt reporting of AEs and unanticipated problems involving risk to subjects or others have been established by our IRB and will be adhered to for all aspects of this project. Any member of the study team will report any unexpected event or problem and any AE, either serious or non-serious, to the PI immediately upon discovery. The PI will then proceed to report the event within the specified timeframes mandated by the DSMB Charter, the IRB and the NHLBI. Any non-serious AE, either study or not study related, can be reported by the research team at the date of the next continuing review. Current regulations require that any AE that is (1) unexpected (in terms of nature, severity, or frequency) given (a) the research procedures that are described in the study-related documents, and (b) the characteristics of the subject population being studied, (2) related or possibly related to study participation, AND (3) suggesting that the research places subjects or others at greater risk of harm than was previously known must be reported to the IRB within 5 business days. A SAE that is non-study related can be reported at the next continuing review.

13 SAFETY ASSESSMENTS

The monitoring in place for assessing the subject's responses will ensure that any untoward change in physiologic status is immediately known.

This includes the following:

1. Measuring pulmonary function at the beginning of each visit and measuring bronchodilator response if there is a drop $\geq 10\%$ from baseline.
2. Obtaining ACT scores at each visit to assess subjects' asthma control.
3. Performing an abbreviated physical exam at all visits.
4. Checking vital signs, including pulse oximetry, to ensure the subject is at their baseline.
5. Asking about interim history to ensure the subject has not had an asthma exacerbation since the previous visit.

As a result of the study design, subjects will be monitored on a case-by-case basis by the study coordinator. The experimental design has each subject extensively monitored; any manner of medical intervention is immediately available, and the appearance of any suspected untoward effect will result in cessation of protocol procedures if decided by the principal investigator.

Any applicable safety concerns will be reported as described above.

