3 STUDY OBJECTIVES

3.1 PRIMARY OBJECTIVE:

- Determine if slow-release DHEA in patients with asthma improves quality of life based on ACQ/ACT scoring.

3.2 SECONDARY OBJECTIVE:

- Determine if slow-release DHEA increases FEV₁ in patients with asthma.
- Determine if SR DHEA in patients with asthma increases the change in pulmonary functions post maximum bronchodilator challenge.
- Determine if slow-release DHEA in patients with asthma decreases FeNO.
- Evaluate the safety and tolerability of DHEA in asthma.
 - Safety outcomes include changes in:
 - Adverse events (AEs)
 - Serious adverse events (SAEs)
 - Pulmonary function (FEV₁, FVC, FEV₁/FVC, FEF25-75)

(An asthma exacerbation (physician decision to treat) will be considered an event of particular interest. Exacerbations not admitted to the hospital will be considered an AE. Exacerbations requiring admission will be considered a SAE.)

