4 STUDY DESIGN

This is a randomized, double-blind, placebo-controlled, cross-over study to determine if DHEA-S will increase FEV₁ and decrease FeNO.

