6 SCHEDULED EVENTS

Assessments and Procedures	Visit 0	MCT	Visit 1	Visit 2	Visit 3	Visit 4	Visit 5	Visit 6
	Screening Day 0	Anytime between days 1-7; at least 3 days prior to Visit 1	Day 7 ± 3 days	Day 21 ± 3 days (phone visit)	Day 35 ± 3 days	Day 63 ± 3 days	Day 77 ± 3 days (phone visit)	Day 91 ± 3 days
Informed consent	X							
Medical history and demographics	X							
Concomitant medications	X		X	X	X	X	X	X
Review inclusion/exclusion criteria	X							
Asthma Control Test (ACT) & Asthma Control Questionnaire (ACQ)	X		X	X	X	X	X	X
Height	X							
Weight, pulse oximetry, vital signs	X	X	X		X	X		X
Urine pregnancy test (when applicable)	X	X	X		X	X		X
Urine cotinine test	X							

Assessments and Procedures	Visit 0	MCT	Visit 1	Visit 2	Visit 3	Visit 4	Visit 5	Visit 6
	Screening Day 0	Anytime between days 1-7; at least 3 days prior to Visit 1	Day 7 ± 3 days	Day 21 ± 3 days (phone visit)	Day 35 ± 3 days	Day 63 ± 3 days	Day 77 ± 3 days (phone visit)	Day 91 ± 3 days
Prostate specific antigen test ¹ (when applicable)	X							
Spirometry with bronchodilator response (maximum bronchodilator)	X							
Spirometry. If ≥ 10% decrease in FEV ₁ from baseline, give bronchodilator and measure response			X		X	X		X
Methacholine Checklist ^a		X						
Methacholine Challenge Test (MCT) (Asthma Participants Only) ^a		X						
FeNO	X		X		X	X		X
Abbreviated physical exam	X		X		X	X		X
Blood draw	X		X		X	X		X
DHEA/placebo capsules dispensed in labeled bottle			X			X		
Collect any unused DHEA/placebo capsules					X			X
Adverse events	X	X	X	X	X	X	X	X
Give Dosing & Symptom Diary			X			X		

¹ This test is for male subjects only. The prostate specific antigen is a protein made by the prostate and found in blood. If the result of this test is >4 nanograms per milliliter, subjects will be informed they are unable to participate in the study. We will also call them prior to their next visit to let them know and recommend that they follow-up with their regular primary care physician.

Assessments and Procedures	Visit 0	MCT	Visit 1	Visit 2	Visit 3	Visit 4	Visit 5	Visit 6
	Screening Day 0	Anytime between days 1-7; at least 3 days prior to Visit 1	Day 7 ± 3 days	Day 21 ± 3 days (phone visit)	Day 35 ± 3 days	Day 63 ± 3 days	Day 77 ± 3 days (phone visit)	Day 91 ± 3 days
Collect Dosing & Symptom Diary					X			X

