8 DESCRIPTION OF VISITS

Below are the visits and the interventions that may occur at each of the visits. In addition to the following scheduled visits, we are also including an unscheduled visit that may be used for any reason when a subject needs to return to the study site to complete study activities.

Visit 0 (Screening Visit)

1. Review the study with the subject and obtain written informed consent and HIPAA authorization
2. Assign the subject a unique subject id number
3. Complete asthma control test and asthma control questionnaire
4. Record demographics and other baseline data

5. Record medical and surgical history, including a history of asthma, diagnosis date, and asthma signs and symptoms
6. Record concomitant medications
7. Review inclusion/exclusion criteria
8. Measure and record height and weight without shoes
9. Perform and record vital signs, including blood pressure after the subject has been seated for 5 minutes
10. Perform and record oximetry
11. Perform abbreviated physical exam
12. Obtain urine to perform urine pregnancy test (when applicable) and urine cotinine test
13. Obtain blood for prostate specific antigen test (when applicable)
14. Perform spirometry with maximum bronchodilator response
15. Perform FeNO
16. Obtain blood
17. Record any adverse events (AEs) that may have occurred since signing consent
18. Schedule MCT or Visit 1

MCT Visit, if needed (Anytime between days 1-7, must be at least 3 days prior to Visit 1)

1. Confirm ongoing consent to participate
2. Collect urine for pregnancy test if applicable
3. Record vital signs and weight
4. Complete MCT checklist
5. Perform and record MCT
6. Confirm eligibility criteria
7. Record adverse events
8. Schedule Visit 1

Visit 1 (Day 7 ± 3)

1. Complete asthma control test and asthma control questionnaire
2. Review and record any changes to concomitant medications
3. Record any adverse events (AEs) that may have occurred since last visit
4. Measure and record weight without shoes
5. Perform and record vital signs, including blood pressure after the subject has been seated for 5 minutes
6. Perform and record oximetry
7. Perform abbreviated physical exam
8. Obtain urine to perform urine pregnancy test (when applicable)
9. Perform spirometry
10. Perform FeNO
11. Obtain blood
12. Give subject a dosing and symptom diary and instructions on dosing intervals
13. Randomize to receive placebo or DHEA-S
14. Send home with 28 days of DHEA-S or placebo capsules
15. Schedule visit 2

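### At Visits 1, 3, 4 and 6 FeNO is listed after spirometry and its conditional bronchodilator, so the condition under which FeNO is measured can depend on FEV₁, another outcome

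*Protocol*

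**What the plan says.** FeNO and FEV₁ are both efficacy outcomes. Section 4 describes the trial thus: "This is a randomized, double-blind, placebo-controlled, cross-over study to determine if DHEA-S will increase FEV₁ and decrease FeNO". Section 3.2 makes each a secondary objective: "Determine if slow-release DHEA increases FEV₁ in patients with asthma" and "Determine if slow-release DHEA in patients with asthma decreases FeNO".

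Three places bear on the order of the two tests:

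- **Section 6, schedule.** One row covers spirometry at Visits 1, 3, 4 and 6. If FEV₁ is down by 10% or more from baseline, the same row tells staff to "give bronchodilator and measure response". FeNO is a separate row, lower in the table.
- **Section 8, visit lists.** Visit 1 has "9. Perform spirometry" followed by "10. Perform FeNO". The two are also adjacent, in the same order, at Visit 3 (items 10 and 11), Visit 4 (items 9 and 10) and Visit 6 (items 9 and 10). At Visit 0, item 14 is "Perform spirometry with maximum bronchodilator response" and item 15 is FeNO.
- **Section 13, item 1.** The safety assessments include "Measuring pulmonary function at the beginning of each visit and measuring bronchodilator response if there is a drop" of at least 10%.

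The FeNO description in Section 7 explains the manoeuvre but gives no timing relative to spirometry or to a bronchodilator.

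**The concern.** A site that works down the lists will do spirometry, give a bronchodilator if FEV₁ has fallen enough, repeat the forced manoeuvres, and then measure FeNO. A subject whose FEV₁ has held up has FeNO taken with no bronchodilator and no second set of manoeuvres. The measurement condition of one outcome is then set by another outcome, after randomisation.

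The trial's hypothesis is that DHEA raises FEV₁. If that is right, the trigger should be met less often at the end of the DHEA period than at the end of the placebo period. If a bronchodilator or the repeat manoeuvres also move FeNO, the within-subject FeNO difference contains a part that comes from the measurement condition and not from airway inflammation.

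Later analysis cannot repair this. If the only FeNO reading at a visit was taken after the bronchodilator, the reading before it does not exist. Adjusting for bronchodilator use would mean conditioning on a post-randomisation variable driven by an outcome.

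**Working it through.** The plan states no figure on this point, so there is nothing to reproduce. The check has two parts.

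**1. Do the sections agree that spirometry comes first?**

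| Source | What it implies |
|---|---|
| Section 8, Visits 1, 3, 4, 6 | Spirometry directly before FeNO |
| Section 6 | Bronchodilator belongs to the spirometry row; FeNO row is lower |
| Section 13 item 1 | Pulmonary function opens the visit |
| Section 7, FeNO | No timing given |

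Sections 8 and 13 disagree on where spirometry falls within the visit, since the treatment-phase lists put it ninth or tenth, after questionnaires, vital signs and examination. On spirometry relative to FeNO they point the same way, and no section puts FeNO first.

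**2. How large could the effect be?**

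For a contrast of end-of-period values (Visits 3 and 6):

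bias in the DHEA-minus-placebo FeNO difference = b × (p_DHEA − p_placebo)

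Here b is the relative shift in FeNO caused by the bronchodilator and repeat manoeuvres, and p is the share of subjects who met the trigger at the end of that period. Neither is in the documents. Assume |b| of 5% to 20% and an absolute difference in use of 0 to 0.30. With 30 subjects (Section 4.2):

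| Difference in use | Subjects of 30 | b = 5% | b = 10% | b = 20% |
|---|---|---|---|---|
| 0 | 0 | 0% | 0% | 0% |
| 0.05 | 1.5 | 0.25% | 0.5% | 1% |
| 0.10 | 3 | 0.5% | 1% | 2% |
| 0.20 | 6 | 1% | 2% | 4% |
| 0.30 | 9 | 1.5% | 3% | 6% |

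The range is 0% to 6% of FeNO, for example 0.30 × 20% = 6%. In any single affected subject the shift is the full b.

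The direction is also open. If use is lower on DHEA and the bronchodilator lowers FeNO, placebo values are pulled down and a DHEA benefit is understated. If it raises FeNO, the benefit is overstated.

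For scale, with 30 complete pairs the standard error is 1/√30 = 0.18 of the SD of the within-subject difference. The difference detectable with 80% power at two-sided 5% is (1.96 + 0.84)/√30 ≈ 0.51 SD, by normal approximation. The protocol gives no SD for FeNO, so the percentages above cannot be placed on that scale.

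If FeNO is measured before spirometry and any bronchodilator, the path through p is closed and this bias is 0 whatever b is.

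**The case against.** The strongest reply is that the order is inferred. Section 8 introduces its lists as things that may happen at each visit, and never says the numbers are a sequence. Read literally, they do not work as one: Visit 1 puts dosing instructions (item 12) before randomisation (item 13), and Visit 0 puts blood for PSA (item 13) and other blood (item 16) on either side of spirometry and FeNO. The lists for Visits 1, 3, 4 and 6 do not mention a bronchodilator. Section 13 item 1 does not mention FeNO, and its reference to each visit would take in the telephone visits, which have no spirometry. This stands in part: a reader might infer that FeNO is in fact taken after the bronchodilator, but the documents support only that the listed order leads there and that nothing prevents it.

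A reader might also infer that the FeNO contrast is confounded. That is too strong. Treatment order is randomised and each subject is scheduled for both treatments. Spirometry precedes FeNO in both periods, so its own effect is common and would largely cancel. What remains is the conditional bronchodilator with its repeat manoeuvres, and that matters only if use is unequal and FeNO responds. No section says that a bronchodilator or forced expiration changes FeNO, so the existence, size and direction of the effect are assumptions.

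Finally, a reader might object that FeNO at Visit 0 always follows albuterol and so cannot be compared with later visits. The treatment contrast does not need Visit 0: Visits 1 and 4 give pre-dose FeNO for each period, Visits 3 and 6 give the end values, and nothing names Visit 0 as the FeNO baseline.

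Within-visit test order is often left to an operating procedure. Here, however, the protocol prints an order, and it is the less favourable one.

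**Conclusion.** The point holds in a limited form. The printed order at Visits 1, 3, 4 and 6 allows the FeNO measurement condition to vary with FEV₁, an outcome the drug is expected to change, and no text requires FeNO first. The contrast is open to outcome-dependent measurement bias; it is not shown to be biased.

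The size is 0% to 6% of FeNO under the assumed ranges, and exactly zero if bronchodilator use is equal in the two periods or if FeNO does not respond to it. The estimate rests on assumed values for both quantities and on sites following the listed order. One secondary outcome is affected, and no sample-size or power figure changes. The change is worth making because it costs almost nothing and the lost readings could not be recovered afterwards, not because a large bias has been demonstrated.

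**What to change.** - In the Section 8 lists for Visits 1, 3, 4 and 6, place FeNO before spirometry and before any bronchodilator. Do the same at Visit 0 for consistency.
- State that order once in the FeNO description in Section 7.
- Record any bronchodilator use before FeNO at each visit.
- Reconcile the wording of Section 13 item 1 on when in the visit pulmonary function is measured with the visit lists, which already place other assessments ahead of it.

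The spirometry safety check and the trigger for the bronchodilator stay as written.

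The cost is two items reordered in five visit lists, one sentence in Section 7, one added data field and a wording change in Section 13. No equipment, visit or test is added. Spirometry would follow one further breath test, so whoever owns the safety section should agree the reconciled wording.

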14 ADVERSE EVENTS AND SEVERITY GRADING

The IU IRB and the FDA have well-established policies (and means) for prompt reporting of AEs and unanticipated problems involving risk to subjects and these policies will be strictly followed.

Adverse and serious adverse events (AE and SAE, respectively) will be defined according to FDA and OHRP guidelines as per IU IRB and NIH requirements.

14.1 ADVERSE EVENT ASSESSMENT

All adverse events will be reported to the Indiana University IRB and FDA as required per their adverse event reporting policies. At the time of the annual review of the study, adverse events will be reported as per the Indiana University HRPP Reportable Events Policy and Guidance. An Adverse Reaction Reporting Form will be completed for any serious and unexpected adverse reaction associated with the study, and the Indiana University IRB will be notified per IU HRPP Reportable Events Policy and Guidance.

An IND safety report will be submitted to the FDA for an event that is a (1) suspected adverse reaction, (2) serious, and (3) unexpected, per FDA guidance.

Suspected adverse reaction means any adverse event for which there is a reasonable possibility that the drug caused the adverse event. For the purposes of IND safety reporting, 'reasonable possibility' means there is evidence to suggest a causal relationship between the drug and the adverse event.

An adverse event or suspected adverse reaction is considered "serious" if, in the view of either the investigator or sponsor, it results in any of the following outcomes: Death, a life-threatening adverse event, inpatient hospitalization or prolongation of existing hospitalization, a persistent or significant incapacity or substantial disruption of the ability to conduct normal life functions, or a congenital anomaly/birth defect. Important medical events that may not result in death, be life-threatening, or require hospitalization may be considered serious when, based upon appropriate medical judgment, they may jeopardize the patient or subject and may require medical or surgical intervention to prevent one of the outcomes listed in this definition.

An adverse event or suspected adverse reaction is considered "unexpected" if it is not listed in the investigator brochure or is not listed at the specificity or severity that has been observed; or, if an investigator brochure is not required or available, is not consistent with the risk information described in the protocol.

Any unexpected fatal or life-threatening suspected adverse reaction will be submitted as an IND safety report to the FDA within seven (7) calendar days after initial receipt of information. Any potential serious risks (serious and unexpected suspected adverse reactions, findings from other studies, findings from animal or in vitro testing, or increased rate of occurrence of serious suspected adverse reactions) will be submitted as an IND safety report to the FDA within fifteen (15) calendar days after initial receipt of the information.

All adverse events will be classified and recorded according to the NCI Toxicity Grading Scale. All study related toxicities will be graded (Grades 1, 2, 3 or 4) according to the Toxicity Grading Scale and will be employed along with potential study drug specific toxicities in the individual subject stopping rules. Subject and study stopping rules will be determined by the DSMB. If the DSMB recommends that the study change or be closed early for patient safety reasons or for slow accrual, the PI will act to implement the change as expeditiously as possible. If a recommendation is made to change the study for other than patient safety reasons or slow accrual, the DSMB will provide an adequate rationale for its decision.

Adverse events will be graded as follows:

Grade 0 – No adverse effects
Grade 1 - Mild adverse events
Grade 2 – Moderate adverse events
Grade 3 – Severe adverse events
Grade 4 – Life threatening or disabling adverse events
Grade 5 – Death related to adverse events

Adverse events will be assessed using the NCI Common Toxicity Criteria guidelines listed in (<http://ctep.cancer.gov/forms/CTCAEv3.pdf>) along with potential study drug specific toxicities in the individual subject stopping rules.

Deaths will be reported to the Indiana University IRB per their institutional guidelines if they occur within 30 days of study intervention. The principal investigator will be responsible for reporting adverse effects to the IRB and other relevant bodies.

14.2 TRACKING OF EVENTS

The following AEs are discussed in the protocol, are discussed with patients as part of the informed consent process, and will be tracked as part of the protocol:

- Complications of venipuncture, blood draw.
- Complications related to study drug

14.3 ADVERSE EVENT REPORTING

- Every event that is reported to either the PI or the designated research associates by the subject or medical staff caring for the subject and which meets the criteria will be documented.
- An AE report will be generated for each event and each report will include: (1) description of the event; (2) when it was reported; (3) severity; and (4) a determination of attribution.
- All SAE's will be reported once the event has been verified, and determination of attribution has been completed in accordance with IU IRB reporting requirements and DSMB requirements. All other AEs will be reported according to the IU IRB reporting requirements.

DSMB requirements are that SAE's be reported to the board within 24 hours of learning of the confirmed event. DSMB will proceed to review, discuss and convey recommendations.

14.4 FOLLOW UP FOR ADVERSE EVENTS

Subject follow-up will be on a case-by-case basis as directed by the PI and/or the IU IRB and the DSMB as appropriate.

15 STUDY MONITORING

This is a single-site investigator-initiated study, taking place at University Hospital on the IU Indianapolis campus. This site will be monitored by representatives from the Indiana Clinical and Translational Sciences Institute. The Investigator grants permission to the monitoring office, and appropriate

regulatory authorities to conduct on-site monitoring and/or auditing of all appropriate study documentation.

